a The last day of dosing will be at Week 36 visit; subject should consume their last dose of study drug on site, after pre-dose assessments have been completed. The Week 36 visit will also be the ET visit. During the study visit, assessments should be collected from any subject who discontinues study drug or study prematurely. Early termination visits will have the same procedures as the Week 36 visit, except that study drug will not be administered and trough PK will not be collected.

b The first day study drug is taken is considered Baseline (Day 1). Day 1 assessments should be performed prior to study drug administration. If a subject requires a transfusion on this day, the transfusion may occur only after all study assessments are completed.

c Qualified site personnel will contact the subject by telephone at Week 2 to capture potential TEAEs and concomitant medications. Subjects will also be reminded of compliance with drug and the next visit schedule. If any AEs of significant clinical concern are identified during the telephonic visit, the subject will be requested to come into the site to be assessed.

d Pharmacogenomic evaluation is optional and may be performed at screening if subject provides informed consent.

e Disease history should contain a confirmed diagnosis of  $\beta$ -thalassemia or hemoglobin E/ $\beta$ -thalassemia. Concomitant alpha gene deletion, duplication, or triplication is allowed.

f After obtaining signed informed consent, the subject's transfusion history for the 12 weeks prior to Baseline (Day 1) visit date should be recorded. In order to be eligible for the study, the dates of transfusion events and the number of pRBC units per event within the 12 weeks prior to the Baseline (Day 1) visit must be available. If available, the following data should also be collected for each transfusion event: volume and hematocrit of each pRBC unit, pre-transfusion Hb, and pre-transfusion weight.

g Vital signs include heart rate, respiratory rate, blood pressure, and body temperature. At Day 1 and Week 3, vital signs will be taken pre-dose and 2 hours ( $\pm$  20 minutes) post-dose, during the PK assessments. At all other timepoints, vital signs can be taken irrespective of taking study drug. Vital signs should be consistently measured in either the sitting or semi-supine position.

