Note: Unscheduled visits may occur, limited to visits resulting from potential TEAEs, drug dispensation, or other urgent study-related procedures.

a The last day of dosing will be at Week 36 visit; subject should consume their last dose of study drug on site, after pre-dose assessments have been completed. The Week 36 visit will also be the ET visit. During the study visit, assessments should be collected from any subject who discontinues study drug or study prematurely. Early termination visits will have the same procedures as the Week 36 visit, except that study drug will not be administered and trough PK will not be collected.

b The first day study drug is taken is considered Baseline (Day 1). Day 1 assessments should be performed prior to study drug administration. If a subject requires a transfusion on this day, the transfusion may occur only after all study assessments are completed.

c Qualified site personnel will contact the subject by telephone at Week 2 to capture potential TEAEs and concomitant medications. Subjects will also be reminded of compliance with drug and the next visit schedule. If any AEs of significant clinical concern are identified during the telephonic visit, the subject will be requested to come into the site to be assessed.

d Pharmacogenomic evaluation is optional and may be performed at screening if subject provides informed consent.

e Disease history should contain a confirmed diagnosis of β-thalassemia or hemoglobin E/β-thalassemia. Concomitant alpha gene deletion, duplication, or triplication is allowed.

f After obtaining signed informed consent, the subject's transfusion history for the 12 weeks prior to Baseline (Day 1) visit date should be recorded. In order to be eligible for the study, the dates of transfusion events and the number of pRBC units per event within the 12 weeks prior to the Baseline (Day 1) visit must be available. If available, the following data should also be collected for each transfusion event: volume and hematocrit of each pRBC unit, pre-transfusion Hb, and pre-transfusion weight.

g Vital signs include heart rate, respiratory rate, blood pressure, and body temperature. At Day 1 and Week 4, vital signs will be taken pre-dose and 2 hours ( $\pm$  20 minutes) post-dose, during the PK assessments. At all other timepoints, vital signs can be taken irrespective of taking study drug. Vital signs should be consistently measured in either the sitting or semi-supine position.

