If one or more results for a variable are assigned to the same analysis visit, the result with the date closest to the protocol scheduled day will be used in the analysis. If 2 measurements in the same analysis visit window are equidistant from the protocol scheduled study day, the earliest measurement will be used in the analysis. If multiple assessments are available on the same day (for the same time point), then the average of the assessment will be used in the analysis. If both central and local assessments of the same lab test are available for the same visit, the central result will take precedence over the local result if baseline is collected centrally. If a scheduled assessment is missing, due to clotting for example, and an unscheduled retest assessment is available in the visit window for the scheduled visit, the unscheduled retest assessment may be used in place of the missing scheduled assessment.

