13.6.2.3 Vital Signs

Descriptive statistics (N, mean, SD, median, Q1, Q3, minimum, and maximum) will be used to summarize vital sign parameters (body temperature, systolic blood pressure, diastolic blood pressure, heart rate, and respiratory rate) at Baseline, each post-Baseline visit, and change from Baseline to each post-Baseline visit, by treatment arm and the combined IMR-687 treatment arms, for both populations. Study Baseline as defined in Section 10.1.2 will be used.

Potentially clinically significant (PCS) post-baseline vital signs can be identified using the criteria shown in the table below. The number and percentage of subjects with any post-baseline treatment-emergent potentially clinically significant vital sign value will be tabulated by treatment group for each criterion. Any subject with a post-baseline result meeting the criteria, including those collected at unscheduled visits, will be counted.

Potentially clinically significant (PCS) post-baseline vital signs can be identified using the criteria shown Table 6 below. The number and percentage of subjects with any post-baseline treatment-emergent potentially clinically significant vital sign value will be tabulated by treatment arm and the combined IMR-687 treatment arms and will be provided separately for each population for each criterion. Any subject with a post-baseline result meeting the criteria, including those collected at unscheduled visits, will be counted.

Table 6 PCS Criteria for Vital Signs

Vital Signs	
Parameter	Criteria
Heart Rate	
 • ≤ 50 and decrease ≥ 15 bpm • ≥ 100 bpm and increase ≥ 15 bpm • ≥ 120 and increase ≥ 15 bpm
SBP	
 • ≤ 90 and decrease ≥ 20 mm Hg • < 140 mmHg and increase ≥ 20 mmHg • ≥ 140 mmHg and increase ≥ 20 mmHg • ≥ 160 and increase ≥ 20 mm Hg
DBP	
 • ≤ 50 and decrease ≥ 15 mm Hg • < 100 mmHg and Increase ≥ 20 mmHg • ≥ 100 mmHg and Increase ≥ 20 mmHg • ≥ 100 mmHg and increase ≥ 15 mm Hg

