A plot will be presented to show the pattern of the SBP and DBP values over time by treatment arm and the combined IMR-687 treatment arms. Mean and SE will be presented in the plot. Additionally, spaghetti plots for SBP and DBP values over time will be provided for 1) individual subjects with maximum post-baseline SBP increased ≥ 20 mmHg and SBP ≥ 150 mmHg and 2) maximum post-baseline DBP increased ≥ 20 mmHg and DBP ≥ 100 mmHg. A shift plot displaying shifts from Baseline heart rate ≤ 100 to maximum heart rate >100 post-Baseline will be provided for each population.

All vital signs will be listed in a data listing. All vital sign tables and listings will be reported on the Safety Analysis Set.

13.6.2.4 12-lead ECGs

The average of triplicate 12-lead ECGs will be performed to evaluate the change from Baseline in ECG parameters (heart rate, PR interval, RR interval, QRS duration, QT interval, and QTcF interval). Descriptive statistics (N, mean, SD, median, Q1, Q3, minimum, and maximum) of ECG parameters will be presented for Baseline, each post-Baseline visit, and change from Baseline to each post-Baseline visit by treatment arm, and the combined IMR-687 treatment arms, for both populations. Study Baseline defined in Section 10.1.2 will be used. At Baseline and Week 3 (TDT Population)/Week 4 (NTDT Population), descriptive statistics will also be presented for change from pre-dose to post-dose. All measurements, including those during unscheduled visits, will be provided in data listings, but only the scheduled measurements will be included in the summary.

The average of the ECG results by visit and parameter will be calculated if two or more of the triplicate ECG values are reported at the visit for baseline or post-baseline visits.

The number of subjects whose baseline or post-baseline QTcF values have exceeded the selected Criteria below, will be summarized with the number and percentage of subjects meeting each criterion, by treatment arm, and the combined IMR-687 treatment arms, and visit (baseline, post-baseline), separately for each population. Subjects with baseline or post-baseline (including unscheduled visits) results meeting any criteria will be counted.

Table 7 PCS Criteria for ECGs

ECGs	Criteria
Parameter	Criteria
QTcF Interval	
 • > 450 msec (males only) • > 470 msec (females only) • > 500 msec
QTcF Interval Increase from Baseline	
 • ≥ 30 msec • ≥ 60 msec

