8. Multiple assessments for the same visit	Vital Sign, ECG and Laboratory assessments	
 All ECG assessments are to be performed in triplicate. Valid assessments will be averaged to get the analysis value for that visit. Other than for ECG assessments, the last non-missing measurement taken prior to the date/time of first study drug (including unscheduled assessments) will be the analysis Baseline. Windowing will be applied for by-visit analyses. Unscheduled or Screening visits that occurred before the Baseline visit will not be assigned an analysis visit. The early discontinuation visit will be eligible for allocation to an analysis visit.

Category	Description	Data Handling Rule
		
 • If one or more results for a variable are assigned to the same analysis visit, the result with the date closest to the protocol scheduled day will be used in the analysis. If 2 measurements in the same analysis visit window are equidistant from the protocol scheduled study day, the earliest measurement will be used in the analysis. • If multiple assessments are available on the same day (or for the same time point for ECG assessments), then the average of the assessments will be used in the analysis. • If both central and local assessments of the same lab test are available on the same day, the central result will take precedence over the local result. • All data will be listed in data listings.
9. Special Lab Value Handling	Lab values with a prefix such as: '>', '<', '+' and 'Less than' Etc.	
 • '>': use the available original value +0.001 in the analyses. • '<': use the available original value -0.001 in the analyses. • '+': use the available original value without the prefix in the analyses. • '≥': use the available original value in the analyses. • '≤': use the available original value in the analyses.

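### The SAP gives two conflicting rules for same-day vital signs, so the 2 h post-dose readings are blended or possibly dropped at Week 3/4, and mean post-dose blood-pressure change is summarised nowhere

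*SAP*

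**What the plan says.** **Collection.** Protocol Table 2, footnote g (TDT): "At Day 1 and Week 3, vital signs will be taken pre-dose and 2 hours" after the dose. Protocol Table 3, footnote g (NTDT): "At Day 1 and Week 4, vital signs will be taken pre-dose and 2 hours" after the dose. At every other visit the timing of vital signs relative to dosing is left free, so these pairs are the only timed post-dose vital signs in the trial.

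**Selecting one value per visit.** The SAP states the same-day rule twice, in different terms.
- Appendix 3 item 8, which covers vital signs, ECGs and laboratory tests: "If multiple assessments are available on the same day (or for the same time point for ECG assessments), then the average of the assessments" is used. The time-point limit is attached to ECGs only.
- Section 10.1.10: "If multiple assessments are available on the same day (for the same time point), then the average of the assessment will be used". Here the time-point limit applies to every variable. The tie rule in the same paragraph says that when two values in a window are "equidistant from the protocol scheduled study day, the earliest measurement will be used in the analysis".

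**Baseline.** Appendix 3 item 8: "Other than for ECG assessments, the last non-missing measurement taken prior to the date/time of first study drug" is the analysis Baseline. In SAP Tables 1 and 2 the Baseline window is Study Day 1 or earlier, and the Week 1 window opens on Day 2.

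**Tables.** Section 13.6.2.3 summarises vital signs "at Baseline, each post-Baseline visit, and change from Baseline to each post-Baseline visit", with no pre-dose/post-dose split. Section 13.6.2.4 does provide one for ECGs: at Baseline and Week 3/4, "descriptive statistics will also be presented for change from pre-dose to post-dose".

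**The concern.** Change from Baseline in vital signs is part of the primary safety endpoint (Protocol Table 1; SAP section 9.0). The 2 h readings were scheduled to see what happens after a dose, yet the SAP has no vital-sign table for that, and its rules for reducing each visit to one value disagree about what becomes of them.

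Two things are at stake. First, two programmers working from different sections of the same SAP could produce different Week 3/4 rows in a primary-endpoint table. Second, an average post-dose shift in blood pressure could be diluted or absent in the by-visit summaries, and also in the mean systolic and diastolic plots if these use the same windowed values.

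**Working it through.** The SAP states no figure on this point, so there is nothing to reproduce. The check follows the rules through each visit and then puts in illustrative numbers.

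**Week 3 (TDT) or Week 4 (NTDT).** Let *base* be Baseline, *pre* and *post* the two readings on the visit date, and D = post − pre.

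- Appendix 3 item 8: visit value = (pre + post)/2, so change = (pre − base) + D/2.
- Section 10.1.10, tie rule applied to the pair: both readings share a date, so they are equally far from the scheduled day and the earlier one is used. Change = pre − base, and D drops out.
- Section 10.1.10, each time point handled separately: the post-dose value survives selection, but section 13.6.2.3 specifies no table to show it.

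The first two routes differ by D/2 for the same subject.

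Illustration for heart rate, assuming base = pre = 80 bpm and a range of rises D. These values are assumptions, not figures from the documents.

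| D (bpm) | By-visit change, Appendix 3 | By-visit change, 10.1.10 tie rule | ECG pre-dose to post-dose table | Raw value meets Table 6 (≥100 bpm and rise ≥15)? |
|---|---|---|---|---|
| 5 | 2.5 | 0 | 5 | no |
| 10 | 5 | 0 | 10 | no |
| 15 | 7.5 | 0 | 15 | no |
| 20 | 10 | 0 | 20 | yes |
| 30 | 15 | 0 | 30 | yes |

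The ECG column assumes that the ECG heart rate shows the same rise as the vital-sign reading.

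The by-visit arithmetic is the same for blood pressure: a 10 mmHg rise becomes (0 + 10)/2 = 5, or 0. There is no counterpart to the ECG column, because no ECG parameter measures pressure. The systolic rise criteria in SAP Table 6 start at 20 mmHg, and the diastolic ones at 20 mmHg, or 15 mmHg where the reading is at least 100 mmHg. A uniform 10 mmHg shift would meet none of them.

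**Day 1.** The pre-dose reading is Baseline. The post-dose reading has Study Day 1, so Tables 1 and 2 put it in the Baseline window, but the Baseline definition stops before the first dose. It is neither Baseline nor assigned to a post-Baseline visit. Nothing is averaged and nothing is reported; the reading simply has no row.

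**Where the raw post-dose values can still appear.**
- Heart rate: the ECG table in section 13.6.2.4, at the same visits and the same nominal 2 h.
- Heart rate and blood pressure: Table 6 counts any qualifying post-baseline result. The heart-rate shift plot and the individual pressure plots select on post-baseline maxima. All vital signs are listed.
- Mean blood-pressure change at 2 h, by arm: no table or figure.

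**The case against.** The strongest reply is that the main cardiovascular question is already answered. Protocol section 5.2.2.3 is chiefly about heart rate. Heart rate is among the ECG parameters, and section 13.6.2.4 tabulates its pre-dose to post-dose change by arm and pooled, from triplicate tracings at nominally the same time. A reader might infer that the safety tables cannot show a post-dose heart-rate effect; the documents do not support that. This part of the objection stands in full.

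It can also be said that the tie rule was written for values on different dates, since it follows a rule about the closest date, and that the time-point wording in section 10.1.10 implies separate handling. That is a fair reading. The loss of the whole effect at Week 3/4 is therefore possible rather than certain. The halving under Appendix 3 does not depend on it.

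Two further inferences should be resisted. Day 1 is not reported as zero change, because there is no Day 1 post-baseline row. Nor do the by-visit tables show trough values throughout, because vital signs at the other visits may be taken at any time relative to the dose.

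Finally, section 5.2.2.3 reports no observable change in blood pressure or pulse in the interim analysis of the sickle cell study, the safety analysis is descriptive, and the DMC may see unblinded vital signs. These points lower the urgency. They do not settle which same-day rule applies or supply the missing blood-pressure summary.

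**Conclusion.** The point holds in a limited form. The two same-day rules conflict, and under the one written specifically for vital signs the Week 3/4 by-visit value is a pre-dose/post-dose blend that carries half of any 2 h effect. Under section 10.1.10 it may be the pre-dose value alone. The Day 1 post-dose reading has no by-visit row, and whether it counts as post-baseline in Table 6 is not stated. Mean 2 h heart-rate change is covered by the ECG tables; mean 2 h blood-pressure change by arm is covered nowhere.

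The halving follows from the rule for any size of effect. The zero rests on applying the tie rule to two readings on one date. The bpm and mmHg figures are illustrations, and the documents give no expected post-dose effect. The change should be made before database lock because it concerns a primary-endpoint table, but it does not put the safety assessment as a whole in doubt.

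**What to change.** 1. Reword section 10.1.10 and Appendix 3 item 8 identically, so that averaging and tie-breaking act only among values at the same nominal time point, for vital signs as for ECGs.
2. State that the Week 3/4 row of the by-visit vital-sign tables uses the pre-dose value.
3. Add to section 13.6.2.3 a descriptive summary, by arm and for the pooled active arms, of the change from pre-dose to 2 h post-dose at Day 1 and Week 3 (TDT) or Week 4 (NTDT). Systolic and diastolic pressure are essential; heart rate would complement the ECG table.
4. Confirm that Day 1 post-dose values count as post-baseline in Table 6.

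The cost is SAP wording and one extra table per population. The readings are already scheduled, so no new data are needed.

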## 12. SAFETY MONITORING AND REPORTING

### 12.1.1. Adverse Event and Serious Adverse Event Collection

#### 12.1.1.1. Time Period Adverse Event Collection

All AEs and SAEs, related and unrelated, will be recorded from the signing of informed consent through the end of study safety follow-up visit (Week 40). Events that occur following administration of study drug will be considered TEAEs.

All SAEs will be recorded and reported to the sponsor or sponsor's designee within 24 hours, as indicated in Section 12.1.2.3. The investigator will also submit any updated SAE data to the sponsor within 24 hours of the data being available.

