13.6.2.1 Adverse Events

MedDRA Coding

AEs will be coded using MedDRA (v23.0 or higher).

Treatment-emergent adverse event (TEAE)

A treatment-emergent adverse event (TEAE) is defined as an AE that emerges on or after the initiation of study drug, or an AE that existed pre-treatment and worsened in severity on or after the initiation of study drug, through 30 days after the last dose of study drug. A pre-treatment adverse event is an AE that emerges before the date of initiation of study drug.

Refer to Appendix 3 for handling of partial dates for AEs for the purpose of assigning treatment-emergent flags. In the case where it is not possible to define an AE as treatment emergent or not, the AE will be classified as treatment emergent.

Severity

Severity is classified as Grade 1: Mild, Grade 2: Moderate, Grade 3: Severe, Grade 4: Life Threatening, Grade 5: Death Related to AE, using the Common Terminology Criteria for Adverse Events, v5.0 (CTCAE v5.0). For the AE summary by CTCAE severity grade, an AE with missing CTCAE severity grade will not be imputed. Imputed values will not be included in data listings.

Relationship to Study Treatment

Relationship is classified as “Unlikely/Not related”, “Possible”, “Probably/Likely”, or “Certain/Related” by the Investigator. A “treatment-related TEAE” for the purpose of this summary is defined as a TEAE with relationship to study drug of “Possible”, “Probably/Likely” or “Certain/Related”. For the AE summary by relationship, an AE with a missing relationship to study drug will not be imputed. Imputed values will not be included in data listings.

TEAEs Leading to Discontinuation of Study Treatment

TEAEs leading to discontinuation of study treatment will be identified by action taken with study treatment being recorded as “Drug withdrawn” on the Adverse events CRF.

Serious and Non-Serious TEAEs

Serious adverse events (SAEs) are those events recorded as “Yes” for the question “Was the adverse event serious?” on the Adverse Event CRF.

TEAEs Leading to Death

TEAEs leading to death are those events which are recorded as “Yes” for the question “Did the adverse event result in death?”, or recorded CTCAE Toxicity Grade 5, or with outcome = “Fatal” on the Adverse Events CRF.

TEAEs Leading to Study Discontinuation

TEAEs leading to study discontinuation are those events which are recorded as “Yes” for the question “Did the adverse event cause the subject to be discontinued from the study?” on the Adverse events CRF.

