10. Prior and concomitant, medication / treatment	Prior, concomitant, and post-treatment medication/treatment	
 • Any medication that was used at any time prior to the date of first study drug is a Prior Medication. • Any medication that was used at any time on or after the date of first study drug and within 30 days of the last dose of study drug is a Concomitant Medication. • If the date of first study medication is missing, then the date of randomization is used (as long as the subject is known to have received study drug on at least one day during the study). Otherwise, in the case of missing dates, any period (Prior and Concomitant) that is possible based on the available information should be applied.
11. Adverse event	Missing CTCAE severity (toxicity grade)	For the AE summary by CTCAE severity grade, an AE with missing CTCAE severity grade will not be imputed. Imputed values will not be listed in data listings.
	Missing relationship to study drug	For the AE summary by relationship, an AE with a missing relationship to study drug will not be imputed. Imputed values will not be listed in data listings.
	Treatment-emergent adverse event	
An adverse event is considered treatment-emergent if emerges on or after initiation of study drug, or an AE that existed pre-treatment and worsened in severity on or after initiation of study drug, through 30 days after the last dose of study drug.
 
An adverse event that begins on the same date as the first dose of study drug is treatment-emergent if the AE begins after the time of first dose or if the time of AE onset is unknown.

Category	Description	Data Handling Rule
		
If the AE start date is partial/missing, then
 
 • If AE start date is completely missing, then the AE is considered as treatment-emergent. • If both AE start month and day are missing and AE start year is the same or after the first dose year, then the AE is considered as treatment-emergent. • If AE start day is missing and AE start year and month are the same or after the first dose year and month, then the AE is considered as treatment-emergent. 
Missing/incomplete (partial) AE start and end dates will not be imputed for data listings.

12. Treatment Duration (days)	Treatment Duration (days)	Treatment duration is defined as Date of last dose of a study drug - Date of first dose of a study drug +1.

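### The partial-date rule for adverse events ignores the end date, so an event known to have ended before the first dose can be flagged as treatment-emergent

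*SAP*

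**What the plan says.** SAP 13.6.2.1 gives the substantive definition: "A treatment-emergent adverse event (TEAE) is defined as an AE that emerges on or after the initiation of study drug", or a pre-existing event that worsens from then on, through 30 days after the last dose. It also defines the complement: "A pre-treatment adverse event is an AE that emerges before the date of initiation of study drug". The overall AE summary has a separate row for pre-treatment events. For partial dates the section sends the reader to Appendix 3, and it adds that an event that cannot be classified either way is taken as treatment-emergent.

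Appendix 3, item 11, repeats the definition and then gives three rules for an incomplete start date:

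- Start date wholly missing: "If AE start date is completely missing, then the AE is considered as treatment-emergent".
- Only the year known: treatment-emergent "If both AE start month and day are missing and AE start year is the same or after the first dose year".
- Year and month known: treatment-emergent "If AE start day is missing and AE start year and month are the same or after the first dose year and month".

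End dates appear in item 11 only in connection with listings: "Missing/incomplete (partial) AE start and end dates will not be imputed for data listings".

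For medications, item 10 of the same appendix takes a different approach to missing dates: "any period (Prior and Concomitant) that is possible based on the available information should be applied".

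Protocol 12.1.1.1 sets the start of collection: "All AEs and SAEs, related and unrelated, will be recorded from the signing of informed consent". Protocol 7.1 allows a screening period of up to 28 days.

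**The concern.** An AE that was over before the first dose can neither emerge nor worsen after it, so under 13.6.2.1 it is a pre-treatment event. The three rules in item 11 do not allow for this. If the site recorded when the event ended but not exactly when it began, the rules can flag it as treatment-emergent although the record itself shows that it was not.

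Incidence and severity of AEs is the first component of the primary endpoint (SAP section 9.0), and the treatment-emergent flag decides which events enter most of the AE tables. A programmer who follows Appendix 3 as written moves such an event out of the pre-treatment row and into the TEAE rows.

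**Working it through.** **1. Apply the rules literally.** Assume a first dose on 20 June 2021. The last column adds one condition: an event with an incomplete start date and a known end date before the first dose is not treatment-emergent.

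| AE start | AE end | Item 11 as written | With end-date check |
|---|---|---|---|
| wholly missing | 10 Jun 2021 | TEAE | not TEAE |
| 2021 only | 10 Jun 2021 | TEAE | not TEAE |
| Jun 2021, no day | 10 Jun 2021 | TEAE | not TEAE |
| May 2021, no day | 10 Jun 2021 | not TEAE | not TEAE |
| 8 Jun 2021 | 10 Jun 2021 | not TEAE | not TEAE |
| wholly missing | unknown | TEAE | TEAE |
| wholly missing | 1 Jul 2021 | TEAE | TEAE |
| Jun 2021, no day | unknown | TEAE | TEAE |

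The first three records are wrong against 13.6.2.1, and the check corrects all three. The other five do not change, including every record whose status cannot be determined. A partial start date in an earlier month or year is not affected.

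**2. How often the rule misfires for an AE that ended before dosing.** Assume that starts are spread evenly over the 28 days before dosing and that first doses are spread evenly over a 30-day month, or over a 365-day year.

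- Day missing: the sum over first-dose day d = 1 to 30 of min(d − 1, 28) is 434; 434 / (28 × 30) = 0.52.
- Day and month missing: the mean lag is 406 / 28 = 14.5 days; 1 − 14.5 / 365 = 0.96.
- Wholly missing: 1.00.

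Events that have already ended tend to have started earlier. If every start is at least 6 days before dosing (illustrative), the day-missing share is 299 / (23 × 30) = 0.43.

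**3. Number of events.** The documents give no rates, so all of these are assumptions: 0.3 screening AEs per subject (0.3 × 120 = 36), 5% to 10% with an incomplete start date, and half to all with a recorded end before dosing.

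- Half ended, day missing: 36 × 0.5 × 0.05 × 0.52 = 0.5, and with 10%, 0.9.
- All ended, 5%, day missing: 36 × 0.05 × 0.52 = 0.9.
- All ended, 10%, wholly missing: 36 × 0.10 × 1.00 = 3.6. This is the extreme case.

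The range is about 0.5 to 3.6 events over both populations and all arms.

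**4. Weight of one subject.** With the arm sizes in SAP 8.1, one subject is 1/30 = 3.3 percentage points of an active arm, 1/20 = 5.0 of the TDT placebo arm and 1/15 = 6.7 of the NTDT placebo arm. The tables count a subject once per system organ class or preferred term. A moved event therefore changes a row only if that subject has no other TEAE in it.

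**The case against.** The best defence is that the body of the SAP already points to the right answer. Item 11 opens with the substantive definition, and 13.6.2.1 keeps the default for events that cannot be classified. A recorded end date before the first dose makes an event classifiable, so the three rules could be read as implementing that default only. This shows the intent, but it does not settle the matter: 13.6.2.1 names Appendix 3 as the place for the flag, and the rules there carry no such limit.

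A second defence is that over-counting is the cautious direction for safety and that the rule treats all arms alike. That is fair when status is unknown, and the fix keeps it. It is no reason to misclassify an event whose status is known, and a misflag on placebo narrows the contrast with active drug.

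Third, the trigger is rare. Protocol 14 and 14.1 require missing data to be explained and queried. Clinically significant laboratory results at screening go to medical history (Protocol 11.3.6). All AEs are listed with dates not imputed, so an affected event can be found. This stands, and it is why the point is small.

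Three stronger readings are tempting:

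- *That treatment-related TEAE counts are inflated as well.* Protocol 12.1.2.2.2 rests causality on the time relationship to drug intake, and an event that ended before any drug fits the unlikely/not related category. A missing relationship is not imputed. Those counts would rarely move.
- *That an arm's TEAE rate shifts by 6.7 points.* That figure applies only to the smallest planned arm, and only if the subject has no other event in the row.
- *That the window for NTDT subjects is generally 42 days.* The extra 14 days need a transfusion between consent and randomization and an approved extension (Protocol 11.1.5).

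**Conclusion.** The point holds as an internal contradiction in the rule that sets the TEAE flag. For an incomplete start date, item 11 gives a wrong flag when the start is wholly missing, or is partial and overlaps the first-dose month or year, and the recorded end date precedes the first dose. This is a stated rule that returns the wrong answer, not a missing detail.

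The consequence is minor. The count cannot be derived from the documents; about one event or fewer, up to a few, is what the assumed rates give. The direction is an over-count of TEAEs in whichever arm the subject belongs to. The documents do not support a claim that the primary safety results would be materially distorted.

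**What to change.** Add to SAP Appendix 3, item 11, ahead of the three rules: *If the AE end date, complete or partial, shows that the AE ended before the first dose of study drug, the AE is pre-treatment whatever the start date; otherwise the rules below apply.* Keep the default to treatment-emergent when status cannot be determined.

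A partial end date settles the matter only if its latest possible value is before the first dose; an end date in the first-dose month with no day leaves the event treatment-emergent. A record whose start falls after its end is a data error and should be queried.

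The cost is one sentence in the SAP and one condition in the program, made before database lock. No correctly classified event changes.
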